#### **3.1.4.1** Imputation of partial missing AE dates

Date and time of AE are mandatory eCRF fields. In the rare cases of missing date, following rules will be applied. Completely missing AE dates are not imputed.

Partial missing AE end dates are imputed as below:

- If the AE is ongoing, the end date is stated to missing.
- If the AE is not ongoing, and:
  - If only the day is missing: Assume the last day of the collected month.
  - If the month is missing: Assume 31-DEC of the collected year.

After applying these rules, if the imputed AE end date is after the end of study date, set the AE end date to end of study date.

Before proceeding with the AE start date imputation, the AE end date is imputed as described above, if necessary.

Only partial AE start dates are imputed. Dates which are completely missing are not imputed. Partial dates are imputed as described below:

- If the day is missing and:
  - If the month and year are different from the month and year of the first dose of IP, assume 01-MMM-YYYY.
  - If the month and year are the same as the first dose of IP month and year and the end date is on or after (including ongoing / missing) the first dose of IP, then assume the date of the first dose of IP.
  - If the month and year are the same as the first dose of IP month and year and the end date is prior to the first dose of IP, then assume the end date.

- If the month is missing and:
  - If the year is different from the year of first dose of IP, assume 01-JAN-YYYY of the collected year.
  - If the year is the same as the first dose of IP year and the end date is on or after (including ongoing / missing) the first dose of IP, then assume the date of the first dose of IP.
  - If the year is the same as the first dose of IP and the end date is prior to the first dose of IP, then assume the end date.

After applying these rules, if the imputed AE start date is after a complete AE end date then assume the same date as the complete AE end date; if the end date is missing and the imputed AE start date is after the end of study date then assume the same date as the study end date.

#### 3.1.4.2 Imputation of partial missing medication dates

Both, completely missing and partially missing concomitant medication start dates are not imputed.

Completely missing medication end dates are not imputed. Partial missing concomitant medication end dates are imputed as below:

- If the medication is ongoing, the end date is set to missing.
- If the medication is not ongoing, and:
  - If only the day is missing: Impute with the last day of the collected month.
  - If the month is missing: Impute with  $31^{st}$  of December of the collected year.

#### 3.1.4.3 Imputation of partial missing COPD history dates

Only partial COPD history dates will be imputed. Dates which are completely missing will not be imputed.

Partial start dates will be imputed as described below:

- If only day is missing, then impute the first day of the month;
- If the month is missing, then impute 1st of January of the collected year.

Partial end dates will be imputed as described below:

- If only day is missing, then impute the last day of the month;
- If the month is missing, then impute 31st of December of the collected year.

#### 3.1.5 Analysis visit windows

For the CCI COPDCompEx related analyses no analysis visit windows will be applied.

For PK related analyses no analysis visit windows will be applied and the actual visits/timepoints will be used instead.

Visit windows will be used for all scheduled assessments to allow for by-visit analyses, since not all assessments are performed on the scheduled day. Unless specified otherwise, all efficacy and safety analyses will be based on the analysis visit windows. The actual assessment day will be mapped to the planned study visit following the analysis visit windowing rules below:

- If more than one assessment falls within a visit window, the closest non-missing assessment to the scheduled day will be used in the analysis.
- If more than one non-missing assessment actual dates are equidistant from the target day, the earlier assessment will be used in the analysis.
- If screening and re-screening visits have same date and time then the re-screening assessment will be used in the analysis.

The visit windows will be calculated by bisecting the scheduled visit days. The lower limit of each window will be the mean of the 2 adjacent planned study days, rounded up to the nearest integer, except for the first post-treatment visit, which will start at 2. The upper limit of each window will be the mean of the 2 adjacent planned study days, rounded down to the nearest integer.

Protocol Visit	Week	Analysis Visit	Scheduled Study Day	Visit Window for Analysis (Days)
SV3	Week 0	Baseline	1	All assessments prior to the first administration of investigational product
SV5	Week 2	Visit 5, Week 2	15	All assessments on or after the first administration of investigational product to 22
SV6	Week 4	Visit 6, Week 4	29	23 to 43
SV7	Week 8	Visit 7, Week 8	57	44 to 71

# Table 7Analysis visit windows for pre-BD clinic spirometry, physical
examination, vital signs, nasal swab for SARS-CoV-2 nucleic acid test

Protocol Visit	Week	Analysis Visit	Scheduled Study Day	Visit Window for Analysis (Days)
SV8	Week 12	Visit 8, Week 12	85	72 to 99
SV9	Week 16	Visit 9, Week 16	113	100 to 127
SV10	Week 20	Visit 10, Week 20	141	128 to 155
SV11	Week 24	Visit 11, Week 24	169	156 to 183
SV12	Week 28	Visit 12, Week 28	197	184 to 211
SV13	Week 32	Visit 13, Week 32	225	212 to 239
SV14	Week 36	Visit 14, Week 36	253	≥240

BD = Bronchodilator; SARS-CoV-2 = Severe acute respiratory syndrome coronavirus 2; SV = Study Visit.

For vital signs, the analysis visit will be "Day 1" for the post-dose assessment done the day of the first administration.

Table 8	Analysis visit windows for serum chemistry, haematology, coagulation
	(except fibrogen), CCI

Protocol Visit	Week	Analysis Visit	Scheduled Study Day	Visit Window for Analysis (Days)
SV3	Week 0	Baseline	1	All assessments prior to the first administration of investigational product
SV5	Week 2	Visit 5, Week 2	15	All assessments on or after the first administration of investigational product to 22
SV6	Week 4	Visit 6, Week 4	29	23 to 57
SV8	Week 12	Visit 8, Week 12	85	58 to 113
SV10	Week 20	Visit 10, Week 20	141	114 to 169
SV12	Week 28	Visit 12, Week 28	197	170 to 211
SV13	Week 32	Visit 13, Week 32	225	212 to 239
SV14	Week 36	Visit 14, Week 36	253	≥240

SV = Study Visit.

#### Table 9 Analysis visit windows for immunogenicity assessments

Protocol Visit	Week	Analysis Visit	Scheduled Study Day	Visit Window for Analysis (Days)
SV3	Week 0	Baseline	1	All assessments prior to the first administration of investigational product
SV5	Week 2	Visit 5, Week 2	15	Start of first administration of investigational product to 22

Protocol Visit	Week	Analysis Visit	Scheduled Study Day	Visit Window for Analysis (Days)
SV6	Week 4	Visit 6, Week 4	29	23 to 57
SV8	Week 12	Visit 8, Week 12	85	58 to 113
SV10	Week 20	Visit 10, Week 20	141	114 to 155
SV11	Week 24	Visit 11, Week 24	169	156 to 183
SV12	Week 28	Visit 12, Week 28	197	184 to 211
SV13	Week 32	Visit 13, Week 32	225	212 to 239
SV14	Week 36	Visit 14, Week 36	253	≥240

SV = Study Visit.

Table 10Analysi	s visit windows for ECGs
-----------------	--------------------------

Protocol Visit	Week	Analysis Visit	Scheduled Study Day	Visit Window for Analysis (Days)
SV3	Week 0	Baseline	1	All assessments prior to the first administration of investigational product
SV8	Week 12	Visit 8, Week 12	85	All assessments on or after the first administration of investigational product to 141
SV12	Week 28	Visit 12, Week 28	197	142 to 225
SV14	Week 36	Visit 14, Week 36	253	≥226

ECG = Electrocardiogram; SV = Study Visit.

#### Table 11 Analysis visit windows for urinalysis and SGRQ assessments

Protocol Visit	Week	Analysis Visit	Scheduled Study Day	Visit Window for Analysis (Days)
SV3	Week 0	Baseline	1	All assessments prior to the first administration of investigational product
SV6	Week 4	Visit 6, Week 4	29	All assessments on or after the first administration of investigational product to 57
SV8	Week 12	Visit 8, Week 12	85	58 to 141
SV12	Week 28	Visit 12, Week 28	197	≥142

SGRQ = St George's respiratory questionnaire; SV = Study Visit.

# Table 12 Analysis visit windows for airwave oscillometry, weight, SARS-CoV-2 serology test (serum),

Protocol Visit	Week	Analysis Visit	Scheduled Study Day	Visit Window for Analysis (Days)
SV3	Week 0	Baseline	1	All assessments prior to the first administration of investigational product
SV8	Week 12	Visit 8, Week 12	85	All assessments on or after the first administration of investigational product to 141
SV12	Week 28	Visit 12, Week 28	197	≥142

# Table 16Analysis visit windows for echocardiogram, post-BD clinic spirometry
assessments CCI

Protocol Visit	Week	Analysis Visit	Scheduled Study Day	Visit Window for Analysis (Days)
SV1	Week -5 to -4	Baseline	1	All assessments prior to the first administration of investigational product
SV8	Week 12	Visit 8, Week 12	85	2 to 141
SV12	Week 28	Visit 12, Week 28	197	≥142

SV = Study Visit.

#### Table 17Analysis visit windows for cough monitoring

Protocol Visit	Week	Analysis Visit	Scheduled Study Day	Visit Window for Analysis (Days)
SV2	Week -3 to -1	Baseline	1	All assessments prior to the first administration of investigational product
SV8	Week 12	Visit 8, Week 12	85	≥2

SV = Study Visit.

Any data collected at early discontinuation and unscheduled visits will be listed and will be included in the definition of maximum/minimum value. The Early Discontinuation and Unscheduled visits will be included when applying the visit windows to ensure that all available data are used in the analysis.

Daily CCI E-RS: COPD, BCSS, cough VAS etc.) will primarily be summarised and analysed as 4-weekly averages, separately. The assessment period of visit windows will be defined in Table 18.

Table 18Labelling of 4-we	eekly periods for CCI and eDiary variables
4-weekly period	Label
Baseline: as defined in Section 3.1.1	Evening of Day -14 to Morning of Day 1 (Baseline)
Period 1: Evening of Day 1 – Morning of	Day 29 Day 1 – 29 (Week 4)
Period 2: Evening of Day 29 – Morning o	f Day 57 Day 29 – 57 (Week 8)
Period 3: Evening of Day 57 – Morning o	f Day 85 Day 57 – 85 (Week 12)
Period 4: Evening of Day 85 – Morning o	f Day 113 Day 85 – 113 (Week 16)
Period 5: Evening of Day 113 – Morning	of Day 141 Day 113 – 141 (Week 20)

#### CONFIDENTIAL AND PROPRIETARY 33 of 167

JCI

4-weekly period	Label
Period 6: Evening of Day 141 – Morning of Day 169	Day 141 – 169 (Week 24)
Period 7: Evening of Day 169 – Morning of Day 197	Day 169 – 197 (Week 28)
Period 8: Evening of Day 197 – Morning of Day 225	Day 197 – 225 (Week 32)
Period 9: Evening of Day 225 – Morning of Day 253	Day 225 – 253 (Week 36)

For all other assessments, there will be no analysis visit windows, the data will be reported according to CRF visit.

For variables analysed using a 4-weekly period, all the days should be considered.

#### 3.1.6 Analysis timepoints for vital signs

For reporting of analysis timepoints in vital signs summaries and listings, the next time windows will be applied:

Visit	Analysis Visit	Planned timepoint
Screening (SV1), SV5, Follow-up 1 (SV13), Follow-up 2 (SV14)	Baseline / Visit 5, Week 2 / Visit 13, Week 32/ Visit 14, Week 36	NA
First 2 doses of study intervention (SV3	Baseline / Visit Y, Week X	Pre-dose
and SV6)	Visit Y, Week X	Post-dose
	Visit Y, Week X	30 min Post-dose
	Visit Y, Week X	60 min Post-dose
	Visit Y, Week X	120 min Post-dose
SV7 – SV11	Visit Y, Week X	Pre-dose
	Visit Y, Week X	Post-dose
	Visit Y, Week X	30 min Post-dose
	Visit Y, Week X	60 min Post-dose
SV12	Visit 12, Week 28	NA

Table 19Vital signs timepoint labelling

NA = Not Applicable, SV = study visit.

To be noted, that assessment that was done at SV3 pre-dose will be labelled "Baseline – Predose", and the following post-dose assessments at SV3, eg Post-dose, 30 min Post-dose, will have analysis visit label "Day 1".

In case of early discontinuation visit, if the visit falls during an on-treatment visit, the corresponding visit will be assigned for the analysis visit with Pre-dose as timepoint.

#### 3.1.7 Study phase windows

For the purpose of the statistical analysis, the assessments will be allocated to the study phase in which they are collected as reported below.

Table 20	Study phase windows
----------	---------------------

Study phase	Phase Window for Analysis (Days)
Pre-treatment	Prior to the first administration of investigational product (day <1 a )
On-treatment	$\geq$ day 1 b to last dose date plus 28 days (included)
Follow-up	> last dose date plus 28 days

a Includes all measurements collected before first dose of IP. If the measurement is collected on day 1 it cannot be determined if it was done before or after the first dose of IP (due to missing time and/or planned time point), then it will be considered as collected after first dose of IP.

b Includes all measurements collected on the day of first dose of IP, at the time of IP intake and after.

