Urinalysis	X	
Pregnancy test (female participant of childbearing potential only) f		X
CCI		
See CT scan collected as part of the s	afety assessments above	ve
Pandemic impact assessment	X	X

Echocardiogram and CT dates will be scheduled at SV1, to occur post-confirmation of eligibility at SV2.

May be performed on a separate day ahead of study visit if required. The analysis can either be performed locally or centrally.

Only required if a CT scan as part of SV2 is performed. If required must be done prior to CT scan.

AstraZeneca

AE = Adverse event; BD = Bronchodilator; CAT = COPD assessment test; COPD = Chronic obstructive pulmonary disorder; CT = Computed tomography; ECG = Electrocardiogram; ePRO = Electronic patient reported outcomes;  $FEV_1$  = Forced expiratory volume in 1 second; FSH = Follicle stimulating hormone; HIV = Human immunodeficiency disease; IGRA = Interferon gamma release assay; NT-proBNP = N-terminal pro-brain natriuretic peptide; PEF = Peak expiratory flow; SAE = Serious adverse event; SARS-CoV-2 = severe acute respiratory syndrome coronavirus 2; SGRQ = St George's Respiratory Questionnaire; SV = Study visit; TB = Tuberculosis.

Table 3 Schedule of Activities: Study Intervention and Follow-up

Study Period					Interver	ition Peri	od				Follo	ow-up		
Visit Number	SV3	SV4 TC	SV5	SV6	SV7	SV8	SV9	SV10	SV11	SV12	SV13	SV14		
Study Day (SV5 to SV14 window: ± 3 days)	1	2	15	29	57	85	113	141	169	197	225	253		
Study Week	0	0	2	4	8	12	16	20	24	28	32	36	E/D	E/A a
Efficacy assessments	•	•		ļ.		ļ.						•		
Clinic spirometry (pre-BD)	X		X	X	X	X	X	X	X	X	X	X	X	
Clinic spirometry (post-BD)						X	4		O *	X			X	
Airwave oscillometry	X					X	4			X			X	
Use of at home spirometry b and eDiary c		Every day throughout inter ention and follow-up periods												
Assess adherence to the completion of eDiary entries and home device use (including PEF)	X	X	X	X	X	х	X	X	X	X	X	X	X	X
Cough monitoring (24 hour monitoring post clinic visit)			D		) >	X								
CCI														
ePRO: SGRQ	X			X		X				X			X	
CCI													'	
Study Participant Feedback Questionnaire (Optional)	X					X						X	X	
Assessment of COPD exacerbations	X	X	X	X	X	X	X	X	X	X	X	X	X	X
Safety assessments		•		l.		l.							1	
Physical examination a, c	X		X	X	X	X	X	X	X	X	X	X	X	X
Weight	X					X				X			X	
ECG	X					X				X		X	X	
Vital signs d	X		X	X	X	X	X	X	X	X	X	X	X	

Table 3 Schedule of Activities: Study Intervention and Follow-up

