# 5.3 Lifestyle Considerations

Participants must abstain from donating blood and plasma from the time of informed consent, and for 16 weeks (5 half-lives) after last dose of study intervention.

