#### E 2 **Definitions**

#### Potential Hy's Law (PHL)

Aspartate aminotransferase or ALT  $\geq$  3 × ULN together with TBL  $\geq$  2 × ULN at any point during the study following the start of study medication irrespective of an increase in ALP.

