AO = Airwave Oscillometry; AX = Area of reactance; BCSS = Breathlessness, cough and sputum scale; COPD = Chronic obstructive pulmonary disease; COPDCompEx = COPD Composite Exacerbations; E-RS:COPD = Evaluating Respiratory Symptoms of COPD; PK = Pharmacokinetic; R5 = Resistance at 5 Hz; R20 = Resistance at 20 Hz; SGRQ = St. George's Respiratory Questionnaire; VAS = Visual analogue scale.

Objectives	Endpoints
CCI	
-	
-	
-	

Objectives	Endpoints
CCI	
CCI	

Table 4Safety objectives and associated endpoints

Objective	Endpoint
To assess the safety and tolerability of MEDI3506	During the intervention and follow-up periods:
compared with placebo in participants with COPD	• AEs, SAEs, AESIs.
and chronic bronchitis.	• Vital signs.
	• Clinical chemistry, haematology, and urinalysis.
	• ECGs.
	• LVEF as measured by echocardiogram.
	• NT-proBNP.
	
 
For participants testing positive for SARS-CoV-2 (by nucleic acid or serology test),
 

Objective	Endpoint
	during the intervention and follow-up periods, the number and proportion of patients with COVID-19 AEs/SAEs and the proportion asymptomatic.
	• Number of participants seropositive for SARS-CoV-2 at end of study who were seronegative at randomization visit.

AE = Adverse event; AESI = Adverse event of special interest; COPD = Chronic obstructive pulmonary disease; COVID-19 = Coronavirus disease 2019; ECG = Electrocardiogram; LVEF = Left ventricular ejection fraction; NT-proBNP = N-terminal pro-brain natriuretic peptide; SAE = Serious adverse event; SARS-CoV-2 = severe acute respiratory syndrome coronavirus 2.

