#### 4.2.10.3 Analysis of laboratory measurements

Laboratory evaluations (continuous haematology, clinical chemistry, urinalysis and coagulation results as per Table 22) will be summarised with descriptive statistics at each visit and change from baseline summarised for each post-baseline visit. Categorical urinalysis results will be summarised in shift tables comparing maximum value during treatment to baseline value. Shifts from baseline to maximum value during treatment in haematology, clinical chemistry, urinalysis and coagulation results will be presented using low, normal and high categories. Laboratory measurements will also be summarised based on the number and percentage of participants above or below a pre-specified threshold for each test, and a listing on key participant information supporting the summary will be provided.

Continuous haematology, clinical chemistry, urinalysis and coagulation results baseline versus maximum observation on treatment will be presented in figures using shift plots.

In addition to the summaries above also the maximum on-treatment ALT and AST by maximum total bilirubin for assessing Hy's law criteria will be presented using the following categories:

Liver Function Parameters	Category
	• $\geq 3 \times - < 5 \times ULN$
ALT	• $\geq 5 \times - <10 \times \text{ULN}$
	• $\geq 10 \times \text{ULN}$
	• $\geq 3 \times - < 5 \times \text{ULN}$
AST	• $\geq 5 \times - <10 \times \text{ULN}$
	• $\geq 10 \times ULN$
T = 4 = 1 1 ; 11;1 ;	• $<2 \times ULN$
l otal bilirubin	• $\geq 2 \times \text{ULN}$
Potential Hy's law	• (AST $\ge$ 3 × ULN or ALT $\ge$ 3 × ULN) and (Total Bilirubin $\ge$ 2×ULN) a

Fable 25	Category for Liver Function parameters
----------	---

ULN: upper limit of normal range.

a: It includes all subjects who have ALT or AST $\ge$ 3xULN and total bilirubin  $\ge$ 2xULN, and in which the elevation in transaminases precede or coincide with (that is, on the same day as) the elevation in total bilirubin.

ALT or AST versus total bilirubin, expressed as multiples of ULN as well as liver biochemistry test results over time – participants with elevated ALT or AST, and elevated total bilirubin will be presented in figures. Liver biochemistry results over time will be presented in figures for participants with elevated AST or ALT, and elevated total bilirubin. A separate listing of key information for participants with potential Hy's law will be produced.

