## 4.2.10.6 Other safety tests

NT-proBNP results will be summarised with descriptive statistics at each visit and change from baseline summarised for each post-baseline visit. The summary based on the number and percentage of participants above or below a pre-specified threshold will be produced. NT-proBNP results will be also summarised in shift table comparing maximum value during treatment to baseline value. NT-proBNP results will be listed.

Number and proportion of participants with a negative or positive SARS-Cov-2 serology result at the end of study, who were seronegative at baseline, will be summarised. Number and proportion of participants who received a COVID-19 vaccine during the study will be included in the summary. All SARS-Cov-2 tests results (both PCR and serology) by visit will be listed for As-treated population.

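### The on-treatment cut-off at last dose + 28 days has no visit-window tolerance, so a protocol-compliant SV12 can be classed as Follow-up and drop out of the on-treatment worst-value displays

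*SAP*

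**What the plan says.** SAP Section 3.1.7 allocates assessments in general, not only adverse events, to phases by date. On-treatment runs from Day 1 "to last dose date plus 28 days (included"; Follow-up is anything "> last dose date plus 28 days". No visit tolerance is given.

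Protocol Section 1.3 (Table 3) puts SV11, the last dosing visit, on Day 169 and SV12 on Day 197, under the row label "Study Day (SV5 to SV14 window: ± 3 days". Protocol Section 4.2.3 confirms that the end of treatment is 4 weeks after the last dose. Protocol Section 1.2 makes SV12 the end-of-intervention visit, and Table 3 lists it in the Intervention Period.

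Several safety displays are limited to treatment:

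- SAP Section 4.2.10.3: shift tables and plots for haematology, chemistry, urinalysis and coagulation, and a table of "the maximum on-treatment ALT and AST by maximum total bilirubin for assessing Hy's law criteria".
- SAP Section 4.2.10.4: the shift table of ECG interpretation, baseline against worst on treatment.
- SAP Section 4.2.10.6: "NT-proBNP results will be also summarised in shift table comparing maximum value during treatment to baseline value".

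SAP Section 3.1.5 adds early-discontinuation and unscheduled visits to the maximum and minimum values. It says nothing about a scheduled SV12 that falls after the cut-off.

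**The concern.** The cut-off sits on the nominal day of the visit meant to close the treatment period. Ordinary variation inside the permitted windows therefore decides whether that visit's results count as on-treatment. The same blood sample can be the Week 28 value in the by-visit table and a follow-up value in the shift table: SAP Table 8 keeps chemistry and haematology as Week 28 through Day 211, and SAP Table 10 keeps ECGs as Week 28 through Day 225.

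What is at stake is the reading at the longest exposure in displays built to show each participant's worst value. Protocol Section 2.3.1 names progression of heart failure as a potential risk, monitored in part by NT-proBNP. SAP Section 3.8.6 schedules that test after dosing only at SV8 and SV12, plus an early discontinuation visit if there is one. Without SV12, a completer's shift-table entry rests on Week 12 alone, after three of seven doses, unless an unscheduled sample was taken. The ECG shift table is in a similar position: SV8 would be the only other scheduled on-treatment reading, because SV14 is follow-up. Serum chemistry and haematology are less exposed, since SV5, SV6, SV8 and SV10 also contribute.

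**Working it through.** **Inputs.** SV11 = Day 169, SV12 = Day 197, SV13 = Day 225, each ±3 days (Protocol Table 3). Cut-off = last dose + 28 days, inclusive (SAP Table 20).

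**Nominal gap.** 197 − 169 = 28 days. This reproduces the protocol's 4 weeks and equals the cut-off exactly.

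**SV11 on schedule.** The cut-off is 169 + 28 = Day 197. SV12 on Days 194 to 197 is on-treatment. SV12 on Days 198, 199 or 200, all in window, is Follow-up.

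**All compliant timings.** Let a be the SV11 offset and b the SV12 offset, each from −3 to +3. The gap is 28 + b − a.

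- Smallest: 28 − 3 − 3 = 22 days. Largest: 28 + 3 + 3 = 34 days.
- SV12 is lost when b > a. Of 7 × 7 = 49 pairs, 7 have b = a and the other 42 split evenly, so 42/2 = 21 are lost.
- The clock starts at the actual dose. SV12 on Day 198 is kept if SV11 was 1 to 3 days late. SV12 on Day 197 is lost if SV11 was 1 to 3 days early.

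**Share of participants (assumption, not from the documents).** With independent offsets, uniform over the 7 days, P(b > a) = 21/49 = 43%. If 60% of visits fall on the nominal day and the rest are uniform, the nominal day has probability 0.6 + 0.4/7 = 0.657 and each other day 0.057. Then P(a = b) = 0.657² + 6 × 0.057² = 0.451, and P(b > a) = (1 − 0.451)/2 = 27%. If every visit were on its nominal day it would be 0%.

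**COVID-19 rescheduling.** Protocol Section 4.1.2 allows a visit to move by up to 14 days. With SV11 on schedule the gap can reach 197 + 14 − 169 = 42 days.

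**Alternative limits.**

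| On-treatment ends at last dose + | Pairs with SV12 lost |
|---|---|
| 28 days | 21 of 49 |
| 31 days | 6 of 49 (b − a of 4, 5 or 6: 3 + 2 + 1) |
| 34 days | 0 of 49 |

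The earliest in-window SV13 after the latest in-window SV11 is (225 − 3) − (169 + 3) = 50 days, so a 34-day limit cannot capture it.

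**Is a reading just past 28 days still informative?** Protocol Section 5.3 gives "16 weeks (5 half-lives) after last dose of study intervention", so the half-life is 112/5 = 22.4 days. Assuming simple first-order decline, the fraction remaining is 2^(−28/22.4) = 42% at 28 days and 2^(−34/22.4) = 35% at 34 days.

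**The case against.** The best defence is that 28 days is one dosing interval, that it matches the SAP's exposure and COPDCompEx definitions, and that an on-treatment display is supposed to leave out later readings. That stands as a reason for having a cut-off. It does not explain why the end-of-intervention visit should fall on either side of it according to visit timing.

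It is also fair that little disappears from the report. By-visit summaries and listings are not limited by phase. The QTcF table uses any post-baseline value. The specification of the vital-sign listing in SAP Appendix A (Table 14.3.8.1.2) names SV3 to SV14. AE tables cover intervention and follow-up (SAP Section 4.2.10.1). A table entry changes only if the excluded SV12 value was that participant's maximum. All of this stands and sets the size of the point.

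A reader might infer that a late Hy's law case could be hidden, since the protocol's Appendix E definition applies "during the study following the start of study medication irrespective of an increase in ALP" while the ALT/AST table is on-treatment only. The documents do not support that. The individual potential Hy's law table (SAP Appendix A, Table 14.3.7.5) covers any point in the study, and the over-time liver figure covers elevations at any time. Only the maximum ALT/AST by bilirubin table is affected.

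A reader might also see the QTcF table as a contradiction in the SAP. An any-post-baseline table beside an on-treatment one is better read as a complementary view.

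**Conclusion.** The point holds in a limited form. Applied exactly as written, Table 20 classes a compliant SV12 as Follow-up whenever it falls 29 to 34 days after the actual last dose, and removes it from four groups of displays: laboratory shift tables and plots, maximum ALT/AST by bilirubin, the ECG worst-value shift and the NT-proBNP shift. This assumes that the treatment limits in SAP Section 4.2.10 carry the Table 20 meaning. That section does not cross-refer to Table 20, but no other definition is given for safety assessments.

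Three stronger readings do not follow:

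- That anyone seen a day late loses SV12. Lateness is measured from the actual last dose, not from Day 197.
- That 43% of participants are affected. 21 of 49 counts timing combinations. Any share of participants rests on an assumed visit pattern.
- That the comparison of arms is biased. The rule applies alike to both arms of a blinded trial and no imbalance is shown. The expected harm is that some late worst values go unshown in these displays.

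Participants who stop dosing before SV11 also lose later readings from these displays. That may be intended, and it is not part of this point.

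**What to change.** For assessment-based safety displays, end the on-treatment phase at last dose + 34 days. This keeps every in-window SV12 after an SV11 dose and stops well short of SV13. Add one sentence stating that an SV12 rescheduled under the COVID-19 provision, for a participant dosed at SV11, is also on-treatment. Cross-refer to this rule from SAP Sections 4.2.10.3, 4.2.10.4 and 4.2.10.6. The treatment-emergent AE and COPDCompEx definitions can stay at 28 days.

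Two simpler repairs fall short. Last dose + 31 days still loses 6 of 49 compliant pairs. Extending the phase to the SV12 date for everyone would mislabel participants who stopped dosing early but, under Protocol Section 7.1, keep attending visits.

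Optionally, present the same tables alongside with the worst post-baseline value through SV14. That would match the safety objective in SAP Table 4, which is framed as "During the intervention and follow-up periods".

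The cost is SAP wording and one programming flag, with no new data. The downside is that a few values up to 34 − 28 = 6 days beyond one dosing interval count as on-treatment, or more for a COVID-rescheduled SV12.
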